- d. The study PI ([name]), who is a licensed clinical psychologist, will be on-call at all times, and will provide weekly (and as needed) supervision to research staff. [name] (Center Co-PI) is a clinical geropsychologist and is experienced in working with older adults, including those experiencing emotional distress, and will be available to consult with [name] as needed.

C. Importance of the knowledge to be gained from the proposed research. There is a pressing public health need to find interventions that reduce loneliness in later life, which is associated with significant

morbidity and mortality among older adults who are caregivers. There are no evidence-based interventions for promoting social connectedness in older adult caregivers. Reducing loneliness and promoting connectedness would significantly improve the lives of older adults who are caregivers by improving well-being and promoting health and longevity. Given the minimal risks associated with the proposed research and the substantial gains both to the individual and older adults more broadly, benefits appear to outweigh the risks.

D. Potential benefits to the subjects. All study subjects will receive a behavioral intervention aimed to increase social connectedness and reduce loneliness – an intervention that targets a significant risk factor for reduced well-being, morbidity and mortality. Thus, the potential benefit to the individual may be significant. Subjects may additionally benefit from participating in research interviews and completing the questionnaire measures, as these assessments provide them with the opportunity to be carefully listened to and comprehensively evaluated. They may further benefit from feelings of altruism connected with participation in research designed to better understand the mental health needs and experiences of community-residing older adults.

E. Alternatives to participation. The alternative to participation in this study is not to participate.

REFERENCES

1. Beeson RA. Loneliness and depression in spousal caregivers of those with Alzheimer's disease versus non-caregiving spouses. *Archives of psychiatric nursing*. 2003;17(3):135-43.

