Overview of the Design: We propose a two-arm RCT: participants will be randomized to (a) smartphone-based MBSR app (Headspace) or (b) active control (breathing app) for 14 days. Loneliness and quality of social interactions will be assessed using end-of-day diary surveys at baseline (T1) and 14-days after randomization (T2).

Specific Aims and Hypotheses:

Aim 1. *To examine the feasibility and acceptability of providing a mobile health mindfulness meditation training intervention to caregivers with significant caregiving stress and loneliness.*

H1a-b: We expect 80% of caregivers screened will report willingness to use the mindfulness app and at least 75% of participants will complete mindfulness training (at least 80% of expected engagements with the app).

Aim 2. *To examine whether a mobile health mindfulness meditation training intervention reduces loneliness and improves quality of social interactions.*

H2a-b: Participants randomized to mindfulness will demonstrate greater improvements (vs. control) in loneliness (3-item UCLA Loneliness Scale) and quality of social interactions (level of intimacy, involvement and enjoyment during/immediately following a social interaction) via end-of-day diary surveys on REDCap.

Aim 3. *To examine mechanisms whereby mindfulness meditation training reduces loneliness and improves quality of social interactions.*

H3a-b. Participants randomized to mindfulness will demonstrate greater improvements (vs. control) in the mindfulness skills of acceptance through nonjudgment and non-reactivity (Five-Facet Mindfulness Questionnaire [FFMQ]), emotion regulation (Difficulties in Emotion Regulation Scale [DERS]), and self-compassion (Self-Compassion Scale) at follow-up.

H3c (exploratory): Effects of mindfulness skills on loneliness and quality of social interactions will be mediated by improvements in emotion regulation.

II. CHARACTERISTICS OF THE RESEARCH POPULATION

- A. Number of subjects.** We propose a sample size of 50 older adults, enrolling a total of 63 participants over 13 months, using a 20% attrition rate for enrollment estimates.

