- B. Gender of subjects.** Women will be well-represented in this study. Caregivers in the US are more likely to be women (67%); Caregivers are also more likely to be white, non-Hispanic (67%), while 10% are African American and 8% are Hispanic. Using the 2018 Alzheimer's Disease Facts and Figures along with our local demographic distributions, we plan to target 25% minority and 67% women enrollment. We will use the extensive resources in place to meet our minority recruitment goals (including targeting men for enrollment, as they represent the gender minority in the caregiver population).
- C. Age of subjects.** All subjects will be 50 years of age or older.
- D. Racial and ethnic origin.** Subjects will represent the demographics of the local population of subjects at the community organization, as shown in the following table:

Racial Categories	Female	Male	Female	Male	
American Indian/Alaska Native	0	0	0	0	0
Asian	2	1	0	0	3
Native Hawaiian or Other Pacific Islander	0	0	0	0	0
Black or African American	4	2	1	1	8
White	30	14	2	1	47
More than One Race	2	1	1	1	5
Total	38	18	4	3	63

E. Inclusion Criteria (assessed at the HARP screening assessment)

1. Age \geq 50 years old.
2. English speaking.
3. Caregiver for a community-dwelling family member with ADRD, living with (or in close proximity to) family member with dementia.
4. Elevated caregiving distress: above population mean (>11) on 10-item Perceived Stress Scale (PSS-10) and/or at least moderate caregiver strain (score ≥ 5) on the Modified Caregiver Strain Index (MCSI).
5. Social disconnectedness: UCLA Loneliness Scale: Short Form score of ≥ 5 .
6. Access to e-mail in order to complete the e-consent module in REDCap which will be used in this study.

F. Exclusion Criteria (assessed at the HARP screening assessment)

1. Non-English speaking because our primary community partner agency (Lifespan) cannot currently accommodate non-English speaking clients.
2. Those with significant cognitive impairment on a cognitive screening measure at the HARP screening assessment.
3. In order to test the effects of developing mindfulness skills in a novice population, those with a regular systematic mindfulness meditation or related mind-body practice (>2 times per week) will be excluded.

G. Vulnerable Subjects.

Individuals who are 50 years of age and older with social risk factors for poor mental and physical health outcomes will be included. The results of this study will inform

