future research and clinical interventions aimed at improving mental health treatment for older caregivers.

III. METHODS AND PROCEDURES

A. Design. This study is a two-arm RCT: participants will be randomized to (a) smartphone-based MBSR app (Headspace) or (b) active control (breathing app) for 14 days. Loneliness and quality of social interactions will be assessed using end-of-day diary surveys at baseline (T1) and 14-days after randomization (T2).

The study team will remain vigilant about any further changes that need to be made to study procedures if there are changes to the research reboot guidance found here: <https://www.urmc.rochester.edu/coronavirus/coronavirus-research/guidance-for-researchers/human-subjectsresearch.aspx>

B. Recruitment. Subjects will be recruited via the IRB approved HARP Population Study (RSRB00068059), a research registry run by the current study's Investigators. In compliance with procedures of the Population Study protocol, subjects of the Population Study consent to allow HARP Population Study researchers to share subjects' identifiable data (both name and contact information) with investigators conducting HARP research at the University of Rochester; in addition, they consent to allow their data collected as part of the Population Study to be included in their research record for subsequent HARP studies they participate in, including the current study. All eligible participants will be given information about this study at their HARP phone screen assessment. Contact information is collected and maintained via the IRB approved HARP Database Study. A brochure describing the study will be given to participants in the HARP Population study (brochure is uploaded in the RSRB online application). Information about the study will also be posted on the webpage of a community organization for older adults, www.beyondthenest.com (content to be displayed is uploaded in the RSRB online application) and the URMC Clinical Trials website. Information about this study will also be provided in the ResearchMatch registry. RSRB-approved study brochures describing the study will be posted at clinics and community organizations serving older adults.

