C. Screening. We will utilize a REDCap eligibility screening survey given the relatively low base rate of loneliness, which is our key inclusion criteria, to increase the efficiency of our screening/enrollment process. Information about the study will be provided at the beginning of the survey. Individuals who complete this survey and endorse loneliness (UCLA Loneliness Scale) and at least mild stress will have the option to provide their contact information to share with the Healthy Aging Research Program (HARP) staff to complete the HARP Database (RSRB00067245) and Population Study (RSRB00068059) assessments, which will provide information needed to determine final eligibility for this Mindfulness study, which is part of the Rochester Roybal Center for Social Ties & Aging Research. The link to the eligibility screen will be available via ResearchMatch, the URMC Clinical Trials website, and the URMC website with information about the study.

D. Process of Consent. Eligible participants who are scheduled for a baseline interview (after phone screening) will provide informed consent prior to start of the interview. Consent will be done via telephone or Zoom. E-consent will be done through the REDCap module. An agreed upon security question will be used for the subject to access the E-consent. The informed consent process will be conducted in a manner to facilitate questions from potential study subjects. If a study team member is unable to answer a question, an investigator will be contacted. All questions from potential subjects should be answered prior to signature. Subjects will certify that the information

in the document is correct (which includes their name), and that electronically signing is the equivalent of signing a physical document. Subjects will sign using finger, mouse or stylus. The study coordinator's name and timestamp will be saved in REDCap as their signature. Consents will be stored within REDCap, and a copy will be e-mailed to the subject. No subjects will be involved in research activities unless an investigator or a designated study staff has obtained documentation of legally effective informed consent of the subject. The collection of protected health information (PHI) and questionnaires are considered to be research activities requiring prior documentation of informed consent.

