3. End-of-day diary surveys via REDCap: Subjects will complete end-of-day dairy surveys for 3 days pre-intervention and 3 days post-intervention. The diaries will be completed in REDCap and will ask about subjective experience of loneliness (using the 3-item UCLA Loneliness Scale) and quality of social interactions.
4. Follow-up assessments: 3-days after the 14-day intervention, participants will complete assessment measures from the baseline interview and an evaluation regarding their experience of the study via telephone or Zoom with a Clinical Research Coordinator.

G. Description of Interventions

Mindfulness Intervention. Participants randomized to the mindfulness intervention will complete up to 14 days of an individual mobile health mindfulness-based intervention training (dose based on a recent study of smartphone-based mindfulness training that demonstrated efficacy in reducing loneliness). Participants will be allotted up to 2 weeks to complete all sessions. The mindfulness intervention will be delivered via Headspace, a mindfulness-based smartphone app. Subjects will be instructed to engage with the app's first 10 introductory sessions. These sessions are intended to act as a general introduction to mindfulness meditation and incorporate techniques such as breath awareness and body scanning. Each session will be completed daily, has a duration of approximately 10 minutes, and is guided by a former Buddhist monk. Upon completion of the introductory sessions, additional content for the four final sessions will be accessible, including sessions from the Reframing Loneliness course, which teaches on connectivity, and the Kindness course, which teaches compassion toward self and others. Note: The study team is not evaluating the safety or effectiveness of the app, nor is the app FDA approved.

Breathing Control. Participants randomized to the breathing app control intervention will complete up to 14 days of an individual breathing app. Participants will be allotted up to 2 weeks to complete all sessions. The breathing control intervention will be delivered via Headspace. The intervention is designed to be structurally equivalent to the mindfulness-based study intervention on key common

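### H1a sets its 80% willingness benchmark on caregivers screened without naming the screening stage, while Aim 1 concerns stressed and lonely caregivers, and the Aim 1 analysis rule does not compute willingness at all

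*Combined protocol and SAP*

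**What the plan says.** All references are to the combined protocol and SAP.

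- **Hypothesis.** Section I (Specific Aims and Hypotheses, Aim 1) states H1a as "We expect 80% of caregivers screened will report willingness to use the mindfulness app". Section IV (Data Analysis, Aim 1) repeats it.
- **Population of Aim 1.** The aim is to examine the feasibility and acceptability of providing the app training "to caregivers with significant caregiving stress and loneliness".
- **Eligibility.** Section II.E requires, among other things, elevated distress (PSS-10 above 11 and/or MCSI of at least 5) and "Social disconnectedness: UCLA Loneliness Scale: Short Form score of ≥ 5". It says that these are assessed at the HARP screening assessment.
- **Screening stages.** Section III.C adds a REDCap survey ahead of HARP, "given the relatively low base rate of loneliness, which is our key inclusion criteria". Those who "endorse loneliness (UCLA Loneliness Scale) and at least mild stress will have the option to provide their contact information" can go on to the HARP assessments. Section III.B also recruits from the HARP registry and states no loneliness filter for that route.
- **Instruments.** The phone screen in Section III.F.1 lists the 4-item PSS, the TICS, the AUDIT-C and the 3-item UCLA scale. It lists no question on willingness.
- **Analysis rule.** Section IV assesses hypothesis 1 from the number of subjects and the sessions that each completes. The criteria are 80% of subjects engaging with the app and 75% completing a full dose.

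**The concern.** The benchmark and the aim refer to different groups unless screened is taken to mean the group already found eligible, and the plan does not say so. On a plain reading, anyone who takes the REDCap survey has been screened. If few of them are both lonely and stressed, the willingness rate mostly describes caregivers whom Aim 1 is not about. Section I gives a reason not to assume that the two groups respond alike: it says that the effect of caregiver stress and loneliness on ability to comply is unknown.

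The second gap is between hypothesis and analysis. H1a concerns stated willingness among people screened. The rule in Section IV concerns app use among subjects. These differ in outcome and in denominator, so the planned analysis would leave H1a unanswered.

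Willingness is one of the two benchmarks for Aim 1. The risk is a statement on acceptability in stressed, lonely caregivers that rests on another group or on another measure.

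**Working it through.** **The plan's own figures.** The 80% is an expectation with no derivation, so there is nothing to reproduce for it. The only derivable design figure is enrollment: 50 / (1 − 0.20) = 62.5, rounded up to 63, which matches Section II.A.

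**Model.** Let q be the share of screened caregivers who belong to the Aim 1 population, pT their willingness, and pN the willingness of the others. If everyone screened is asked:

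overall rate = q × pT + (1 − q) × pN

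The documents give none of q, pT or pN. All values below are assumptions, shown over a range.

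**What an overall rate of exactly 80% says about the target group.** With pN free between 0 and 1, pT lies between max(0, (0.8 − (1 − q)) / q) and min(1, 0.8 / q). For q = 0.5 the lower bound is (0.8 − 0.5) / 0.5 = 60%. For q = 0.9 the bounds are 0.7 / 0.9 = 78% and 0.8 / 0.9 = 89%.

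| q | Range of pT if overall is 80% | Overall if pT 60%, pN 90% | Overall if pT 90%, pN 70% |
|---|---|---|---|
| 0.1 | 0–100% | 87% | 72% |
| 0.2 | 0–100% | 84% | 74% |
| 0.3 | 33–100% | 81% | 76% |
| 0.5 | 60–100% | 75% | 80% |
| 0.9 | 78–89% | 63% | 88% |

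At q = 0.25 the two scenarios give 0.25 × 0.60 + 0.75 × 0.90 = 82.5% and 0.25 × 0.90 + 0.75 × 0.70 = 75.0%.

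**Where the misreading stops.** In the first scenario, 0.90 − 0.30q = 0.80 gives q = 1/3, so the benchmark is met despite 60% target willingness up to about q = 0.33. In the second, 0.70 + 0.20q = 0.80 gives q = 0.5, so the benchmark is missed despite 90% target willingness below that share.

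**Sampling variation.** Take 63 target caregivers for illustration.

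- All screened as denominator, q = 0.2: N = 63 / 0.2 = 315, and the benchmark needs at least 252 willing. The first scenario meets it with probability 0.975. The second misses it with probability 0.992.
- Same, q = 0.3: N = 210, at least 168 willing. The probabilities fall to 0.681 and 0.901.
- Target caregivers only, n = 63, at least 51 willing: 60% willingness meets the benchmark with probability 0.0003, and 90% misses it with probability 0.009.

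**Hypothesis and rule side by side.** H1a: outcome is stated willingness, denominator is caregivers screened. Section IV rule: outcome is engagement with the app, denominator is subjects. No value of q reconciles the two.

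**The case against.** The best reply is that H1a does not say all caregivers screened. Section II.E places eligibility at the HARP screening assessment, and entrants from the REDCap route have already endorsed loneliness and at least mild stress. If screened means HARP, the group is enriched and the distortion is small, as the q = 0.9 row shows. This stands as a limit on size. It does not remove the point: the stage is not named, registry entrants have no stated filter, and the REDCap filter is not stated to equal the distress and loneliness criteria.

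It is also fair that the base rate has no figure and concerns loneliness alone, and that the plan does not say in which population it is low. A reader might infer that most of those screened are outside the target group. The documents do not establish that. They support only that many may be, since caregivers who are both stressed and lonely cannot outnumber the lonely ones.

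A further reply is that Section IV uses subjects. If these are enrolled participants, they meet the distress and loneliness criteria, so the screened denominator does not drive the planned result. That is correct. It shifts the defect: what is computed is then not willingness, and people who have already consented would more likely overstate it.

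Two stronger readings are tempting.

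- Because "All eligible participants will be given information about this study at their HARP phone screen assessment", one might say that the rate is capped at the eligible share and that 80% is out of reach. This requires counting people who were never asked as unwilling, which the plan nowhere says. Section III.C also informs every survey-taker at the start, and being informed is not being asked.
- One might add that acceptability after use is ignored, because "an evaluation regarding their experience of the study via telephone or Zoom" enters no Aim 1 analysis. H1b already sets a benchmark on use, so adding that evaluation is a reporting preference and carries no weight here.

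Finally, H1a is an expectation in a pilot, and no progression or stopping decision hangs on it.

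**Conclusion.** The point holds in a limited form. H1a's denominator is undefined as to stage and, read plainly, is wider than the Aim 1 population, so it may misstate willingness in that population. The amount depends on an unknown mix: large if few of those screened are in the target group (at q of 0.2 or less, an overall 80% is compatible with any target rate), small if screened means the enriched HARP stage (78–89% at q = 0.9). The 25% share and the willingness gaps of 30 and 20 points are illustrations with no basis in the documents. A reader might infer that the H1a verdict will be wrong, or is as likely to be wrong in one direction as in the other. The documents show only that it could be.

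The mismatch between hypothesis and analysis rule needs no assumption: as written, Section IV does not compute H1a. Both should be corrected. With no decision tied to H1a, this affects how Aim 1 is interpreted and does not threaten the trial.

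**What to change.** 1. In Section I and Section IV, define H1a as the number willing divided by the number asked, among caregivers who meet the study's eligibility criteria, including those on distress and loneliness, at the HARP screening assessment. Count refusals and non-answers among those asked as not willing.
2. Add one willingness question at that stage and list it in Section III. State there which measure establishes the distress criterion, because the phone screen lists the 4-item PSS and the criterion uses the PSS-10 or MCSI.
3. In Section IV, replace the 80% engagement rule with this calculation. The 75% completion rule for H1b can stay.
4. Report the rate among all screened caregivers who were asked as a secondary description.

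The cost is wording in two sections, one added screening question and one cross-tabulation. The price in precision is modest. At a true rate of 80% the standard error is √(0.8 × 0.2 / 63) = 5.0 percentage points with 63 asked, against √(0.8 × 0.2 / 315) = 2.3 points with 315. Both denominators are illustrative. Treatment, randomization and sample size do not change.

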Mindfulness to Reduce Loneliness in Family Caregivers

NCT04560088

8/29/2022

MINDFULNESS TRAINING TO REDUCE SOCIAL ISOLATION AND FEELINGS OF LONELINESS IN OLDER CAREGIVERS FOR FAMILY MEMBERS WITH ALZHEIMER'S DISEASE AND RELATED DEMENTIAS

Principal Investigator: [name]

RSRB#00005296

I. RATIONALE FOR THE STUDY AND SPECIFIC AIMS

Purpose: The current objective of this pilot study is to provide initial evidence of the role of mindfulness training in improving social disconnectedness – including social isolation and feelings of loneliness – in older caregivers for family members with ADRD.

Background: Social isolation and feelings of loneliness are risk factors for older caregivers for family members with Alzheimer's Disease and Related Dementias (ADRD).¹ Further, social isolation and loneliness place older caregivers at risk of poor health, including increased inflammation, cardiovascular disease, depression, and premature mortality.² Interventions to promote social connectedness in older caregivers have the potential to reduce elevated morbidity and premature mortality and buffer the high caregiving burden in this growing but understudied population. Thus, developing effective treatments to reduce social disconnectedness in older adults is essential, but previous behavioral treatment efforts have had limited success.³ Mindfulness-based interventions may reduce loneliness in older adults, as demonstrated in a randomized controlled trial of an 8-week mindfulness-based stress reduction program.⁴ Another recent study demonstrated the efficacy of a smartphone-based mindfulness training for reducing loneliness and increasing social contact in daily life among adults reporting above average stress;⁵ however, smartphone-based mindfulness training interventions have not been tested with older adults, nor have they been tested with caregivers of family members with ADRD. Specifically, prior studies were conducted with healthy adults not necessarily burdened by caregiving; it remains unknown how caregiver stress -- related to competing demands on time and significant loneliness -- may impact the ability to comply with the intervention as well as indicate barriers to efficacy. The current study will follow a similar protocol as the aforementioned randomized controlled trial that used a smartphone-based mindfulness training to address loneliness and social contact.⁵

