- E. Randomization.** The Center statistician will be responsible for randomizing all participants. To ensure treatment balance, new participants will be sequentially assigned to receive (a) smartphone-based MBSR app (Headspace) or (b) active control (breathing app) using covariate adaptive randomization, which will take into account covariates (i.e., age and gender) and previous assignment of participants. The statistician will then inform the project coordinator of study condition. In all instances, members of the research team responsible for data collection will remain blind to study condition and the statistician will be the only one with access to the randomization schedule.
- F. Assessments.** Data obtained during the assessments will be obtained specifically for research purposes. Participants will complete the standard STAR baseline and follow-up assessments, with the addition of mindfulness (using the Five-Facet Mindfulness Questionnaire [FFMQ]), emotion regulation (using the Difficulties in Emotion Regulation Scale [DERS]), and Self-Compassion Scale

questionnaires. Loneliness (using the 3-item UCLA Loneliness Scale) and quality of social interactions will be assessed daily using end-of-day diary surveys and all baseline measures will be repeated 3 days after the 14-day intervention.

1. Initial eligibility phone screen: verbal informed consent will be conducted; demographics data will be collected (age, gender, race/ethnicity, education, marital status, living arrangements, caregiver status); and screening instruments will be administered (4-item Perceived Stress Scale, cognitive assessment [Telephone Interview for Cognitive Status; TICS], AUDIT-C, and UCLA Loneliness 3-item scale). Those who do not endorse exclusion criteria for cognition and alcohol abuse will be invited for an initial assessment for further assessment for participation in the study.

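### Should an isolation outcome be named, given that the full title and Purpose mention social isolation but no hypothesis does?

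*Combined protocol and SAP*

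**What the plan says.** The full title begins "MINDFULNESS TRAINING TO REDUCE SOCIAL ISOLATION AND FEELINGS OF LONELINESS IN OLDER CAREGIVERS". The Purpose in section I is to "provide initial evidence of the role of mindfulness training in improving social disconnectedness – including social isolation and feelings of loneliness". The Background adds that the study will "follow a similar protocol as the aforementioned randomized controlled trial that used a smartphone-based mindfulness training to address loneliness and social contact". The short title names loneliness only.

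Under Specific Aims and Hypotheses the scope is narrower. Aim 2 is "To examine whether a mobile health mindfulness meditation training intervention reduces loneliness and improves quality of social interactions". H2 measures loneliness with the 3-item UCLA scale, and it measures "quality of social interactions (level of intimacy, involvement and enjoyment during/immediately following a social interaction) via end-of-day diary surveys on REDCap". H1 concerns willingness and completion. H3a-b concern mindfulness skills, emotion regulation and self-compassion. H3c concerns mediation of the Aim 2 outcomes. Section IV (Data Analysis) names the same outcomes aim by aim.

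The entry criterion in II.E item 5 reads "Social disconnectedness: UCLA Loneliness Scale: Short Form score of" 5 or more, so disconnectedness at entry is a loneliness score. In section IV the term appears only as a baseline descriptor.

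Section III.F.2.a lists the Berkman-Syme Social Network Index, the Interpersonal Support Evaluation List and the PROMIS Social Functioning tests in the core battery. Section III.F says that "all baseline measures will be repeated 3 days after the 14-day intervention", and III.F.4 says the same in general terms. The opening paragraph of section IV plans mixed models with time × condition interactions on the diary data and on the baseline-to-follow-up data, without listing outcomes.

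**The concern.** Isolation and loneliness are different constructs: one is how much contact and integration a person has, the other is how that person feels about it. The Purpose lists both. A reader who starts from the title will look for a result on isolation and find none designated. Interaction quality does not supply it, because it rates interactions that took place and does not count them. The isolation domain of the Self-Compassion Scale (III.F.2.f) does not supply it either, because it is a part of self-compassion.

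The stake is selective reporting. At least three repeated measures could later be offered as the isolation result, with none chosen in advance. Two remedies suggest themselves: name the Social Network Index as an Aim 2 outcome, or add a daily diary question on whether social contact occurred.

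**Working it through.** **1. Aims, data and models side by side.**

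| Place | Isolation, network or contact outcome named? |
|---|---|
| Full title, Purpose | Isolation named as a target |
| H1a-b, H2a-b, H3a-b, H3c | No |
| Section IV, Aims 1 to 3 | No |
| Section IV, opening paragraph | None named; baseline-to-follow-up data covered in general |
| III.F.2.a with III.F and III.F.4 | Three social measures scheduled twice |
| III.F.3, diary | Loneliness and interaction quality; form not shown |

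The data and a model for them are therefore in the plan. What is absent is the choice of one measure.

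**2. Sample size.** The plan gives no figure for isolation, and no SD, correlation, alpha or power. Its only sample-size arithmetic reproduces: 50 / (1 − 0.20) = 62.5, rounded up to 63. I assume 50 analysed in equal arms of 25.

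**3. What naming the Social Network Index would yield.** With one value before and one after, and correlation ρ between them (assumed), the standard error of the between-arm difference in change, in SD units, is √[2(1 − ρ) × 2/25].

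- ρ = 0.5: √0.080 = 0.283; × 1.96 = ±0.55 SD
- ρ = 0.7: √0.048 = 0.219; × 1.96 = ±0.43 SD
- ρ = 0.9: √0.016 = 0.126; × 1.96 = ±0.25 SD

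The interval is narrow only if the index hardly moves between visits. The time between visits is short: 3 diary days, 14 intervention days and 3 further days make about 20 days. That agrees with the 3 weeks of follow-up mentioned in the Risk/Benefit Assessment, A.3. In III.F.2.a only the UCLA scale is described as sensitive to change. The index is described by its prediction of morbidity and mortality.

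**4. Cost of leaving the choice open.** If any of three measures could be reported as the isolation result and there is no true effect, the chance of at least one p < 0.05 is 1 − 0.95³ = 0.143 when they are independent and 0.05 when they are fully correlated. Measures grouped under one heading of social connectedness are unlikely to be independent, so 14% is the extreme.

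**5. What a daily contact item would yield.** Take 3 days before and 3 after, a share p of days with contact, and a correlation φ between two days of the same person. The standard error of the between-arm difference in change in that share is √[(2/25) × (2/3) × p(1 − p)(1 − φ)]. I assume a correlation of 0.3 to 0.5 on an underlying normal scale, which gives φ = 0.163 to 0.295 at p = 0.80 and 0.098 to 0.204 at p = 0.95.

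- p = 0.80: SE 0.085 to 0.078; × 1.96 = ±17 to ±15 percentage points
- p = 0.95: SE 0.048 to 0.045; × 1.96 = ±9 percentage points, where the largest possible rise is 5

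A high share is plausible if contact with the care recipient counts, because II.E item 3 requires "living with (or in close proximity to) family member with dementia". The diary form is not shown, and section IV defers the quality ratings to a cited procedure, so contact may already be recorded.

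**The case for a change.** The best case for acting is that it costs almost nothing. Naming one measure before analysis is a line of text on data already scheduled, and it would close off a later choice among three. The general sentence in section IV does not close it, because it names no outcome. Pilot status is not a full answer either: the Purpose still offers initial evidence on isolation, and the request would be for an estimate with an interval, not a powered test. If isolation is not a target, taking it out of the title and Purpose is equally cheap.

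The textual part of this stands: the full title and Purpose are wider than the aims. The rest is weaker. Nothing in the documents favours the index over the two other measures, and it may be the one least able to move in about 20 days, so naming it could produce a null that tells the reader little. A similar protocol to an earlier trial does not commit this one to each of that trial's outcomes. The Specific Aims, the diary and the Aim 2 model agree with one another, and those govern what is tested. Deleting a word from the title would leave every analysis as it is.

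**Conclusion.** The full title and Purpose are broader than the aims, but the plan does not need changing. Followed as written, it gives sound answers on loneliness and interaction quality, which are the outcomes that Aim 2 sets. An analyst can report the repeated social measures together as secondary descriptions under the general time × condition sentence, and no claim in the aims depends on which of them is called isolation.

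The gain from designating one is small and debatable: an interval of ±0.25 to ±0.55 SD on a measure of uncertain responsiveness, against a false-positive risk that rises from 5% to at most 14%, and only if someone picks among three independent measures after seeing the results. A daily contact item has little to offer at high contact rates and rests on a form that is not available to check.

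All of these sizes assume 25 analysed per arm, and the correlations and contact rates are assumptions too, since the documents give none. That the index is collected twice rests on the general statements in III.F and III.F.4, which do not list it by name at follow-up.
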